9.1.1. Primary Endpoint: Time to Complete Eschar Removal

Estimated log hazard ratio from study MW2004-11-02 (SoC versus NexoBrid) = -1.39, using a Cox proportional hazards model with treatment as only covariate.

Standard error = 0.28

Target log hazard ratio = -1.39 + 0.28/2 = -1.25; target hazard ratio $\lambda = 0.29$.

The formula for the number of events D (successful complete eschar removals) is:

$$D = \frac{4(z_{\alpha} + z_{\beta})^2}{(\ln \lambda)^2}$$

(Piantadosi, Clinical Trials: A Methodologic Perspective, p.169)

 $z_{\alpha} = 1.96$;

 z_{β} = 1.28 for 90% power.

If the proportion of events in NexoBrid group is denoted by $p_1 = 0.59$

and the proportion of events in SoC group is denoted by $p_2 = 0.70$,

which are the observed proportions in the study MW2004-11-02, the number of patients required $n = \frac{2D}{p_1 + p_2} = 42$ (to the nearest even number), 21 in each group.

In accordance with the European regulatory requests and planned age distribution, we believe that a sample size of 80 patients per arm will detect with a 90% power a difference on the primary endpoint, which is well within what would be expected, based on the results from the previous study.

Based on the above calculations, we plan a study with total sample size of 160 patients; 80 (NexoBrid) + 80 (SoC)⁵.

9.1.2. Secondary Endpoint: Incidence of Surgical Excision

Estimated proportions having surgical excision from study MW2004-11-02: NexoBrid 0.42; SoC 0.80

Standard errors: NexoBrid 0.057; SoC 0.044

Difference = 0.38; Standard error of difference = 0.073

Anticipated difference: 0.38-0.073/2 ≈ 0.34

We therefore take the anticipated proportion with surgical excision to be: NexoBrid 0.44 and SoC 0.78.

Using Fisher's exact test, the power achieved with a total sample size of 160 patients (80 in each group) using a two-sided significance level of 5% is 99.1%.

Statistical Analysis Plan V02 of 31 May 2021

⁵ Updated calculations were performed to support the final sample size of 145 patients enrolled into the study (provided in 13.3 13.3Update to Study Sample Size Due to COVID-19 Pandemic)

9.1.3. **Secondary Endpoint: Blood Loss**

Estimated mean blood loss from study MW2004-11-02: NexoBrid 421.93 ml; SoC 1024.27 ml

Standard errors: NexoBrid 129.52; SoC 240.98

Difference: -602.33; Standard error of difference: 273.58

Anticipated difference: -602.33 + 273.58 / 2 = -465.54

Using a two-sided two-sample t-test the power with a total sample size of 160 patients and a two-sided significance level of 5% is 58.8%.

Secondary Endpoint: Area of Autograft in DPT Wounds

The proportion of subjects with at least one DPT wound was 62.6% in the study MW2004-11-02. Therefore, if 160 patients are enrolled to the CIDS study, we expect 100 patients to have at least one DPT wound and be thereby eligible for this analysis.

Estimated difference in mean area autograft in DPT wounds from study MW2004-11-02 (NexoBrid vs. SoC) = 13.30-23.63 = -10.33.

Standard error = 6.02

Target difference $\Delta = -10.33 + 6.02/2 \approx -7.32$.

Using a two-sided two-sample t-test the power with a total sample size of 160 patients using a two-sided significance level of 5% is 23.1%.

Secondary Endpoint: Incidence of Autograft in DPT Wounds

Estimated log OR using GEE approach from study MW2004-11-02 (NexoBrid vs SoC): -0.676

Standard Error: 0.40

Anticipated log OR: -0.676+0.40/2=-0.476

Using the normal approximation to the Wald test statistics (see for example Shih (1997)) we obtain a power of 53.3% with a total sample size of 160 patients using a two-sided significance level of 5%.

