11.1.9. Handling of Multiple Comparisons

Unless otherwise specified, all statistical tests will be conducted against a two-sided alternative hypothesis, employing a significance level of 0.05. The primary and secondary endpoints of efficacy will be tested in a hierarchy, so as to preserve the nominal significance levels:

- 1. Primary: time to complete eschar removal
- 2. Secondary: Incidence of surgical excision
- 3. Secondary: Blood loss
- 4. Secondary: Area of Autograft in DPT wounds

5. Secondary: Incidence of Autograft in DPT wounds

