13.3. Update to Study Sample Size Due to COVID-19 Pandemic

According to the study protocol version 9.01 dated 29 July 2019, 160 patients were to be enrolled into the study according to the defined age group distribution. Prior to the outbreak of COVID-19 pandemic and until March 2020, 145 patients were enrolled into the study.

The COVID-19 pandemic significantly affected all study sites' ability to enroll additional patients. There was a great uncertainty regarding when restrictions would be lifted and study sites would be able to resume enrollment. Therefore, MediWound explored whether the recruitment to the study can be completed at this stage, with 145/160 (91%) of patients

enrolled, in line with FDA guidance document: "Statistical Considerations for Clinical Trials During the COVID-19 Public Health Emergency", issued on 17 June 2020.

The original sample size and statistical power calculations for this study were based on effects reached during the first Phase 3 study (MW2004-11-02) which was completed in 2009. Since then MediWound had also completed the recruitment and the 12 month follow up of 175 adult patients randomized to the Phase 3 study MW2010-03-02 (DETECT). Power calculations were performed also using data from this latest phase 3 study.

The updated sample size calculations, presented below, confirmed that based on a sample size of 145 patients, the study is sufficiently powered to meet the primary and main secondary and safety endpoints as originally planned. Thus, the study provides all required data to evaluate NexoBrid's safety and efficacy in pediatric patients while enabling the early availability of the product to address an unmet need in the pediatric population. These power calculations were submitted to the pediatric committee (PDCO) within the EMA and to the FDA to support MediWound's request for early completion of enrollment.

The request for early study completion was endorsed by the study's DSMB, relying on the confirmation that study endpoints can be met with the sample size of 145 patients and pending FDA and EMA approval.

The request for early completion of enrollment was accepted by both the FDA and the PDCO (EMA) and therefore the enrollment of patients into the study was completed with a total of 145 patients, with the following age distribution:

- 45 patients ≥0 months and ≤23 months old
- 30 patients ≥24 months and ≤3 years old
- 50 patients ≥4 years and ≤11 years old
- 20 patients ≥12 years and <18 years old

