Power calculations for MW2012-01-01 study considering a reduced sample size of 145 patients

Sample sizes needed to achieve a power of 90% for the statistical tests in the analysis of MW2012-01-01 (CIDS) are estimated. The calculations are based on the 12 months' data of

the DETECT study (MW2010-03-02), as well as on data from the previous study MW2004-11-02.

Note, that the power calculated for each test does only refer to the power of that specific test. When conducting multiple tests in a hierarchical testing procedure, endpoints which are positioned at later points of the hierarchy, might not be tested if earlier tests do not reject the corresponding null hypotheses. Therefore, the power of the tests in a hierarchical testing procedure also depends on the other endpoints and will be lower.

Time to Complete Eschar Removal

Estimate based on study MW2004-11-02

The sample size calculation based on the results of study MW2004-11-02 assumes that the proportional hazards assumption will be judged appropriate and consequently a Cox model will be used for the primary analysis:

Estimated log hazard ratio from study MW2004-11-02 (NexoBrid versus SoC) = -1.39, using a Cox proportional hazards model with treatment as only covariate.

Standard error = 0.28

Target log hazard ratio = -1.39 + 0.28/2 = -1.25; target hazard ratio λ = 0.29.

The formula for total number of events D is: $D = \frac{4(z_{\alpha} + z_{\beta})^2}{(\ln \lambda)^2}$

(Piantadosi, Clinical Trials: A Methodologic Perspective, p.169)

 $z_{\alpha} = 1.96$;

 z_{β} = 1.28 for 90% power.

If the proportion of events in group 1 is denoted by p1 = 0.59

and the proportion of events in group 2 is denoted by p2 = 0.70

which are the observed proportions in the study MW2004-11-02, the number of patients required per group is $n = \frac{2D}{p_1 + p_2} = 42$ (to the nearest even number), 21 in each group.

Estimate based on study MW2010-03-02

Since the proportional hazards assumption was rejected in study MW2010-03-02 trial, the sample size calculation based in this study assumes that this will also be the case in the CIDS study and consequently a generalized Wilcoxon-Gehan test will be used in the analysis. Based on the data from MW2010-03-02, simulations were conducted, using the generalized Wilcoxon-Gehan-Test for the primary analysis, resulting in a total sample size of 94 (47 per group) needed to achieve a power of 90%.

% Wound Area Surgically Excised for Eschar Removal

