Estimate based on study MW2004-11-02

Estimated difference in mean percent wound excised from study MW2004-11-02 (NexoBrid vs. SoC) = 15.1 - 59.6 = -44.5.

Standard error = 5.3

Target difference $\Delta = -44.5 + 5.3/2 = -41.85$.

The formula for the number of patients per group n is: $n = \frac{2(z_{\alpha} + z_{\beta})^2 \, \sigma^2}{\Delta^2}$

where

 $z_{\alpha} = 1.96$;

 z_{β} = 1.28 for a power of 90%;

 σ = the estimated common standard deviation of percent area of wound excised = 34.

For 90% power, number per group = 14

Estimate based on study MW2010-03-02

Estimated mean % area surgically excised from study MW2010-03-02: NexoBrid 3.66; SoC 58.74

Standard errors: NexoBrid 2.09; SoC 5.78

Difference: -55.08; Standard error of difference = 5.89

Target difference Δ = -55.08 + 5.89/2 ≈ -52.13.

Using a two-sided two-sample t-test with a two-sided significance level of 5%, the total sample size required to achieve a power of 90% is 24 (12 per group).

Incidence of Surgical Excision

Estimate based on study MW2004-11-02

Estimated proportions having surgical excision from study MW2004-11-02: NexoBrid 0.42; SoC 0.80

Standard errors: NexoBrid 0.057; SoC 0.044

Difference = 0.38; Standard error of difference = 0.073

Anticipated difference: 0.38-0.073/2 ≈ 0.34

We therefore take the anticipated proportion with surgical excision to be: NexoBrid 0.44 and SoC 0.78.

Using Fisher's exact test with a two-sided significance level of 5%, the total sample size required to achieve a power of 90% is 96 (48 per group).

Estimate based on study MW2010-03-02

Estimated proportions having surgical excision from study MW2010-03-02: NexoBrid 0.04; SoC 0.72

Standard errors: NexoBrid 0.023; SOC 0.052

Difference = 0.68: Standard error of difference = 0.057

Anticipated difference: $0.68-0.057/2 \approx 0.652$

We therefore take the anticipated proportion with surgical excision to be: NexoBrid 0.05 and SOC 0.70.

Using Fisher's exact test with a two-sided significance level of 5%, the total sample size required to achieve a power of 90% is 26 (13 per group).

Incidence of Autograft in DPT Wounds (wound level analysis)

Estimate based on study MW2004-11-02

Only subjects with at least one DPT target wound will be eligible for this analysis. The expected proportion of subjects with at least one DPT target wound estimated from study MW2004-11-

02 is 62.6%.

Estimated log OR using GEE approach from study MW2004-11-02 (NexoBrid vs SoC): -0.676

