Standard Error: 0.40

Anticipated log OR: -0.676+0.40/2=-0.476

Using the normal approximation to the Wald test statistics (see for example Shih (1997)) we obtain that a total sample size of 1150 patients (720 evaluable) is needed to achieve a power of 90% using a two-sided significance level of 5%. This means that a sample size of 575 subjects per arm would be required to obtain the minimum number of evaluable subjects for

90% power in this endpoint.

Estimate based on study MW2010-03-02

Only subjects with at least one DPT target wound will be eligible for this analysis. The expected proportion of subjects with at least one DPT target wound estimated from study MW2010-03-02 is 58%.

Estimated log OR using GEE approach from study MW2010-03-02 (NexoBrid vs SoC): -0.5078

Standard Error: 0.4988

Anticipated log OR: -0.5078+0.4988/2=-0.5078

Using the normal approximation to the Wald test statistics (see for example Shih (1997)) we obtain that a total sample size of 5880 patients (3410 evaluable) is needed to achieve a power of 90% using a two-sided significance level of 5%. This means that a sample size of 2940 subjects per arm would be required to obtain the minimum number of evaluable subjects for 90% power in this endpoint.

Page 128 of 138

Area of Autograft in DPT Wounds (wound level analysis)

Estimate based on study MW2004-11-02

Only subjects with at least one DPT target wound will be eligible for this analysis. The expected proportion of subjects with at least one DPT target wound estimated from study MW2004-11-

02 is 62.6%.

Estimated difference in mean area Autograft in DPT wounds using GEE approach from study

MW2004-11-02 (NexoBrid vs SoC): -11.41

Standard Error: 4.89

Anticipated difference: -11.41+4.89/2=-8.97

Using the normal approximation to the Wald test statistics (see for example Shih (1997)) we obtain that a total sample size of 486 patients (304 evaluable) is needed to achieve a power of 90% using a two-sided significance level of 5%. This means that a sample size of 243 subjects per arm would be required to obtain the minimum number of evaluable subjects for

90% power in this endpoint.

Estimate based on study MW2010-03-02

Only subjects with at least one DPT target wound will be eligible for this analysis. The expected proportion of subjects with at least one DPT target wound estimated from study MW2010-03-

02 is 58%.

Estimated difference in mean area Autograft in DPT wounds using GEE approach from study

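### The 53.3% power stated for incidence of autograft conflicts with the SAP's own 1150 patients for 90% power; from the same inputs it is about 23% at 160 patients

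*SAP*

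**What the plan says.** Section 9.1.5 of the SAP (numbered so in the table of contents) takes a log odds ratio of -0.676 with standard error 0.40 from MW2004-11-02. It reduces the effect by half a standard error to -0.476 and, using a normal approximation to the Wald test, reports: "we obtain a power of 53.3% with a total sample size of 160 patients using a two-sided significance level of 5" percent.

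Appendix 13.3 repeats the same estimate, standard error, anticipated effect, method and level, and states: "we obtain that a total sample size of 1150 patients (720 evaluable) is needed to achieve a power of 90" percent. It notes that "Only subjects with at least one DPT target wound will be eligible for this analysis" and puts that share at 62.6%. Section 9.1.4 applies the same share to 160 patients: "we expect 100 patients to have at least one DPT wound and be thereby eligible for this analysis".

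For the same endpoint on MW2010-03-02 data, Appendix 13.3 prints "Anticipated log OR: -0.5078+0.4988/2=-0.5078" and then a requirement of 5880 patients (3410 evaluable).

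The appendix sets out its aim as follows: "Sample sizes needed to achieve a power of 90% for the statistical tests in the analysis of MW2012-01-01 (CIDS) are estimated". Its opening text says that, with 145 patients, "the study is sufficiently powered to meet the primary and main secondary and safety endpoints as originally planned".

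Section 11.1.9 places the endpoint at the end of the testing order: "5. Secondary: Incidence of Autograft in DPT wounds".

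**The concern.** With effect, method and significance level fixed, power at one sample size determines the sample size needed for any other power. A trial with 53.3% power at 160 patients cannot need 1150 for 90%. One of the two statements is wrong, and a reader of Section 9.1.5 alone would take the single-test power for this endpoint to be more than twice what the appendix implies. That affects how a non-significant result would be read.

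The same appendix supported closing enrolment at 145. Its summary sentence refers to the main secondary and safety endpoints without saying which they are, while several of the sizes printed below it are far above 145.

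**Working it through.** **Inputs.** Anticipated log odds ratio 0.476 in absolute value and SE 0.40 (Sections 9.1.5 and 13.3); two-sided 5%, so z = 1.960; 90% power, so z = 1.2816 and the sum is 3.2415; 1150 enrolled / 720 evaluable (13.3); evaluable share 62.6% (9.1.4 and 13.3).

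**1. Source size behind the 1150.** Section 9.1.5 does not give the number of patients behind the SE of 0.40, so it is derived from the appendix. The SE needed at 720 evaluable is 0.476 / 3.2415 = 0.147. An SE of 0.40 then corresponds to 720 × (0.147 / 0.40)² ≈ 97 evaluable, or 97 / 0.626 ≈ 155 enrolled. Going forward, 97 × (0.40 × 3.2415 / 0.476)² ≈ 720 evaluable, and 720 / 0.626 ≈ 1150, so the appendix figure is reproduced.

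**2. Power at the trial's size.** Power = Φ(3.2415 × √(N / 1150) − 1.960).
- N = 160: Φ(1.209 − 1.960) = 22.6%.
- N = 145: 20.9%.
- Using the SE of 0.40 unscaled: Φ(0.476 / 0.40 − 1.960) = 22.1%.
- If all 160 patients were evaluable: 33.3%.

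The stated 53.3% is not reproduced by any of these.

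**3. What 53.3% would require.** It needs 1.960 + 0.083 = 2.043 standard errors. The size for 90% power would then be 160 × (3.2415 / 2.043)² ≈ 403, not 1150. The SE at 100 evaluable would be 0.476 / 2.043 = 0.233, and an SE of 0.40 would come from 100 × (0.233 / 0.40)² ≈ 34 evaluable, about 54 enrolled.

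**4. Which figure agrees with the rest of the SAP.**
- The excision standard errors in Section 9.1.2 imply 0.42 × 0.58 / 0.057² ≈ 75 plus 0.80 × 0.20 / 0.044² ≈ 83, about 158 patients. That fits 155 and rules out 54.
- The wound-level autograft area calculation in 13.3 (304 evaluable, difference 8.97, SE 4.89) implies 304 × (8.97 / (3.2415 × 4.89))² ≈ 97 evaluable.
- The 23.1% power for autograft area in Section 9.1.4 is reproduced by a t-test with 97 source and 100 evaluable patients (23.1%).

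All three support the 1150.

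**5. Possible origin.** The unreduced effect of 0.676 gives 40.4% two-sided. With a one-sided 5% test it gives 52.8%, or 51.8% with the SE unscaled. That is close to 53.3% but contradicts the stated two-sided level and the stated effect, and it does not prove how the figure arose.

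**6. The misprint.** −0.5078 + 0.4988 / 2 = −0.2584. With 0.2584 and 3410 evaluable, the SE of 0.4988 corresponds to 3410 × (0.2584 / (3.2415 × 0.4988))² ≈ 87 evaluable. The MW2010-03-02 area calculation (922 evaluable, 6.25, SE 6.28) also gives 87. With 0.5078 the result would be about 336, more than the 175 randomised in that study. Only the printed effect is wrong.

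**7. Totals printed in 13.3 for 90% power, against 145 enrolled.**

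| Endpoint | MW2004-11-02 | MW2010-03-02 |
|---|---|---|
| Time to eschar removal | 42 | 94 |
| Surgical excision | 96 | 26 |
| MVSS, 12 months | 70 | 52 |
| MVSS, 24 months | 98 | 72 |
| Blood loss | 494 | 80 |
| Wound closure | 2164 | 34 |
| Autograft area (wound level) | 486 | 1590 |
| Autograft incidence | 1150 | 5880 |

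**The case against.** The strongest reply is that little depends on the figure. The sample size rests on the primary endpoint, and secondary power is only reported. The 53.3% is single-test power, and Appendix 13.3 itself warns that power within the hierarchy is lower. Autograft area stands just ahead with a stated power of 23.1%, so under the plan's assumptions the chance of formal success at the fifth step could not exceed 23.1% even if 53.3% were right. This stands: the error concerns single-test power and should not be read as a fall in the chance of hierarchical success from one half to one fifth.

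Second, the SAP says its Section 9 calculations come from the protocol and refers to 13.3 for the updated ones. The protocol text available is a synopsis without secondary power, so the origin of the 53.3% cannot be traced. This affects where to correct it, not whether it is wrong.

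Third, 13.3 prints every required size, so nothing is hidden, and naming the endpoints is a matter of clarity. That is fair, but the sentence draws a conclusion from those sizes, and the term main secondary is undefined.

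Fourth, some sizes in the table carry caveats: the MVSS inputs are borrowed across time points, MW2010-03-02 used a different blood loss formula, and the MW2004-11-02 blood loss entry states an SE of 273.58 but uses 267.75. None of these alters the autograft figures.

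**Conclusion.** The point holds. From the inputs in Section 9.1.5 and the sizing in Appendix 13.3, power for incidence of autograft is about 22–23% at 160 patients and about 21% at 145, against 53.3% stated. This assumes, as 13.3 does, that the 62.6% evaluable share and the number of wounds per patient carry over from MW2004-11-02. If all 160 patients were evaluable the power would be 33.3%, still well short of 53.3%.

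The -0.5078 is a misprint for -0.258, and the 5880 is unaffected. On the appendix's own sizes, 145 patients give at least 90% single-test power on both source studies for the primary endpoint, surgical excision and MVSS. For blood loss and wound closure they do so only on MW2010-03-02 inputs. For neither autograft endpoint do they do so on either source.

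This is a correction of stated power that should be made. It does not affect enrolment, the primary sizing, any test or the testing order.

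**What to change.** - **Section 9.1.5:** recompute and replace the 53.3%. Scaling from 13.3 gives about 22–23% at 160 patients and about 21% at 145. State the evaluable share and the source-study size, and say that this is single-test power. If the full protocol carries the 53.3%, correct it there too or add a note explaining the difference.
- **Appendix 13.3, incidence of autograft, MW2010-03-02:** change the printed anticipated log odds ratio from -0.5078 to -0.258 and leave the 5880 as it is.
- **Appendix 13.3, opening text:** name the endpoints for which 145 patients suffice. These are the primary endpoint, surgical excision and MVSS on both source studies, and blood loss and wound closure on MW2010-03-02 inputs only. Say that neither autograft endpoint is covered. Note that the MW2004-11-02 entry for MVSS at 12 months uses a 24-month difference, that the MW2010-03-02 entry for 24 months uses 12-month data, and that MW2010-03-02 used a different blood loss formula.

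The cost is text only: one power figure, one printed value and one sentence with its caveats, plus the matching protocol text if it exists. The stated power for autograft incidence becomes less favourable.

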9.2. Safety Set

The safety set includes all patients who received a treatment and analysis is focused on the treatment actually performed.

9.3. Full analysis Set (Intent-to-Treat population)

The full analysis set (FAS) includes all patients who were randomized into the trial. The analysis is focused on the planned treatment. The analysis of the ITT population (FAS) provides the primary and secondary efficacy and the comparative safety analyses.

9.4. Per Protocol Set

The per protocol (PP) set includes all subjects who do not have major protocol violations (cf. section 8). Analysis of the PP population is for supportive purposes. The PP analysis will include patients in the treatment group according to treatment received.

9.5. Enrolled population

The enrolled population consists of all subjects who passed through the screening processes and signed informed consent.

10. Data Handling

A missing start date of an ongoing concomitant medication or adverse event will be imputed by the date of informed consent.

